4.3 Justification for dose

This study is extended from PANORAMA-HF OLE study, with a similar study design as PANORAMA-HF OLE study. The starting dose of study drug will be determined by the Investigator considering the participant's condition The dose level at the end of study visit of PANORAMA-HF OLE study may remain the same, or the dose level may be changed at the discretion of the Investigator. Maintaining the dose level at the end of study visit in PANORAMA-HF OLE study is considered appropriate, to ensure a smooth transition to this study medication taking safety and tolerability aspects into account. However, since it may not be appropriate to maintain the dose due to changes in the participant's condition, etc., the dose level could be changed at the discretion of the Investigator.

4.4 Rationale for choice of control drugs (comparator/placebo) or combination drugs

Not applicable

4.5 Rationale for public health emergency mitigation procedures

In the event of a public health emergency as declared by local or regional authorities (i.e. pandemic, epidemic or natural disaster), mitigation procedures may be required to ensure participant safety and trial integrity and are listed in relevant sections of the study protocol. Notification of the public health emergency should be discussed with Novartis prior to implementation of mitigation procedures, and permitted/approved by local or regional health authorities and ethics committees as appropriate.

4.6 Purpose and timing of interim analyses/design adaptations

Not applicable

4.7 End of study definition

Study completion is defined as when the last participant finishes their End of study visit and any repeat assessments associated with this visit have been documented and followed-up appropriately by the Investigator or, in the event of an early study termination decision, the date of that decision.

5 Study population

The study population consists of Japanese pediatric HF patients, in-patients or outpatients. Only patients who successfully completed PANORAMA-HF OLE study and fulfill protocol

requirements (see Section 5.1 and Section 5.2) are eligible to participate in this study. Patients in PANORAMA-HF OLE study for whom study medication had been temporarily interrupted during the study (including at the study completion), may be considered for this study if they meet all entry criteria. A maximum of 8 Japanese patients will be enrolled into the study.

5.1 Inclusion criteria

Participants eligible for inclusion in this study must meet all of the following criteria:

- 1. Signed informed consent as well as assent at an appropriate age must be obtained prior to participation in the study.
- 2. Male or female, inpatient or outpatient, and < 18 years of age (at the time of signing informed consent).
- 3. Patients who have completed PANORAMA-HF OLE study and are able to be safely enrolled into this study as judged by the Investigator.

5.2 Exclusion criteria

Participants meeting any of the following criteria are not eligible for inclusion in this study.

- 1. Patients who permanently discontinued the study drug treatment during PANORAMA-HF OLE study.
- 2. Renal vascular hypertension (including renal artery stenosis).
- 3. Patients with a history of angioedema.
- 4. Patients who have parents or legal guardians who do not give consent or allow the child to give assent, or inability of the patient or the parents/legal guardians to follow instructions or comply with follow-up procedures.
- 5. Any medical condition(s) that may put the patient at risk in the Investigator's opinion, or that the Investigator deems unsuitable for the study.
- 6. Patient breastfed by a mother taking ACEI.
- 7. Pregnant or nursing (lactating) female patients.
- 8. Female patients of child-bearing potential, defined as all females physiologically capable of becoming pregnant, **unless** they are using highly effective methods of contraception while taking study treatment and for 7 days after stopping medication. Highly effective contraception methods include:
 - Total abstinence (when this is in line with the preferred and usual lifestyle of the participant. Periodic abstinence (e.g. calendar, ovulation, symptothermal, post-ovulation methods) and withdrawal are not acceptable methods of contraception
 - Female bilateral tubal ligation, female sterilization (have had surgical bilateral oophorectomy with or without hysterectomy) or total hysterectomy at least six weeks before taking study treatment. In case of oophorectomy alone, only when the reproductive status of the female has been confirmed by follow up hormone level assessment.
 - Male sterilization (at least 6 months prior to screening). For female participants on the study, the vasectomized male partner should be the sole partner for that participant

• Use of oral (estrogen and progesterone), injected, or implanted hormonal methods of contraception or placement of an intrauterine device (IUD) or intrauterine system (IUS), or other forms of hormonal contraception that have comparable efficacy (failure rate <1%), for example, hormone vaginal ring or transdermal hormone contraception.

In case of use of oral contraception, females should have been stable on the same pill for a minimum of 3 months before taking study treatment.

Females are considered post-menopausal if they have had 12 months of natural (spontaneous) amenorrhea with an appropriate clinical profile (e.g. age-appropriate history of vasomotor symptoms). Females are considered not of child-bearing potential if they are post-menopausal or have had surgical bilateral oophorectomy (with or without hysterectomy), total hysterectomy or bilateral tubal ligation at least six weeks prior to enrollment on study. In the case of oophorectomy alone, only when the reproductive status of the female has been confirmed by follow-up hormone level assessment is she considered to be not of child-bearing potential.

If local regulations are more stringent than the contraception methods listed above to prevent pregnancy, local regulations apply and will be described in the informed consent form (ICF).

5.3 Screen failures

Participants or parents/guardians who sign an informed consent form for themselves or for their child, respectively, and who (i.e. the participant) are subsequently found to be ineligible for this study, will be considered a screen failure. The reason for screen failure should be entered on the applicable electronic Case Report Form (eCRF). The baseline characteristics at Visit Day1, demographic information, informed consent, and Inclusion/Exclusion pages must also be completed for screen failure participants. No other data will be entered into the clinical database for participants who are screen failures, unless the participant experienced a serious adverse event (SAE) during the screening phase (see SAE section for reporting details).

Participants or parents/guardians who sign an informed consent for themselves or for their child, respectively, and who are considered eligible but fail to be started on treatment on Visit Day1 for any reason may be enrolled in this study. However, they will have to discontinue the study unless the study treatment starts within 3 months from Visit Day1 and will be considered an early study termination. The reason for early study termination should be captured on the appropriate disposition eCRF at Visit EOS.

5.3.1 Participant numbering

Each participant is identified in the study by a Participant Number (Participant No.). The Participant No. consists of the Site Number (Site No.) (as assigned by Novartis to the investigative site) with a sequential participant number suffixed to it, so that each participant's participation is numbered uniquely across the entire database. Upon signing the informed consent form, the participant will be assigned the same Participant Number as he/she had in the PANORAMA-HF OLE study.

6 Study treatment(s) and concomitant therapy

6.1 Study treatment(s)

The sacubitril/valsartan study medication is available in 3 formulations: tablets, granules or liquid formulation (Table 6-1). For liquid formulation, please refer to the Pharmacy Manual.

Table 6-1 Open-label sacubitril/valsartan formulation

Formulation	Strength	Comments
capsule containing 4 granules (3.125 mg/granule)	12.5 mg	capsules in bottles
capsule containing 10 granules (3.125 mg/granule)	31.25 mg	capsules in bottles
tablets	50 mg	tablets in bottles
tablets	100 mg	tablets in bottles
tablets	200 mg	tablets in bottles
liquid quanancian		Prepared from tablets 100 mg
liquid suspension		(please refer to Pharmacy Manual)

All pediatric formulations of study medication (sacubitril/valsartan granules or liquid) will be made available to all participants. The tablet formulations of sacubitril/valsartan will be available for participants based on the participant's dosing and ability to swallow adult tablets (refer to Pharmacy Manual).

An overview of available sacubitril/valsartan formulations is illustrated in Table 6-1. Capsules of sacubitril/valsartan containing 4 granules or 10 granules per capsule will be provided for oral use. The granules can be swallowed by the participant, after the removal of the outer capsule. Participants who cannot use tablets or granules can use the liquid formulation. Sacubitril/valsartan liquid formulation will be compounded by the site / pharmacy (please refer to Pharmacy Manual).

Sufficient medication will be provided for treatment according to the study protocol. Medication labels will be in the local language and comply with the legal requirements of the country. The labels will include storage conditions for the drug, and will not include information about the participant.

Participants taking the liquid formulation of sacubitril/valsartan will need to have a resupply every 4 weeks. Given the burden of traveling to the site for study visits for participants and families, the parent/caregiver can come to the site without the participant for dispensation of study drug between scheduled study visits (see Table 1-2). Delivery of study drug to the participant can also be used, where possible and where allowed by local regulations.

6.1.1 Additional study treatments

No other treatment beyond investigational drug is included in this trial.

6.1.2 Treatment arms/group

There is 1 treatment arm in this open-label study. All participants will receive open-label sacubitril/valsartan.

6.1.3 Treatment duration

The study will continue until marketed product of pediatric formulation is available in Japan.

6.2 Preparation, handling, storage, and accountability

Each study site will be supplied with study treatment in packaging as described under Table 6-1.

Medication will be provided as tablets, granules or liquids. Tablets and granules will be provided by Novartis to the study site. Liquid preparation will be provided by the site For liquid preparation, please refer to Pharmacy Manual.

As per the treatment assigned to the participant, Investigator staff will select the study treatment to dispense to the participant.

As per Section 4.5, during a public health emergency as declared by local or regional authorities i.e. pandemic, epidemic or natural disaster, that limits or prevents on-site study visits, delivery of IMP directly to a participant's home may be permitted (if allowed by local or regional health authorities and ethics committees, as appropriate) in the event the Investigator has decided that an on-site visit by the participant is no longer appropriate or possible, and that it is in the interest of the participant's health to administer the study treatment even without performing an on-site visit. The dispatch of IMP from the site to the participant's home remains under the accountability of the Investigator. Each shipment/provisioning will be for a maximum of 3-months supply. In this case, regular phone calls or virtual contacts (every 4 weeks or more frequently if needed) will occur between the site and the participant for instructional purposes, safety monitoring, investigation of any adverse events, ensuring participants continue to benefit from treatment, and discussion of the participant's health status until the participants can resume visits at the study site.

6.2.1 Handling of study treatment

Study treatment must be received by a designated person at the study site, handled and stored safely and properly and kept in a secured location to which only the Investigator and designated site personnel have access. Upon receipt, all study treatment must be stored according to the instructions specified on the labels and in the Investigator's Brochure.

Clinical supplies are to be dispensed only in accordance with the protocol. Technical complaints are to be reported to the respective Novartis Country Organization Quality Assurance.

Medication labels will be in the local language and comply with the legal requirements of each country. They will include storage conditions for the study treatment but no information about the participant.

The Investigator or designated site staff must maintain an accurate record of the shipment and dispensing of study treatment in a drug accountability log. Monitoring of drug accountability

will be performed by field monitors during site or remote monitoring visits, and at the completion of the trial. The Investigator must provide accountability also for locally sourced materials used for administration (e.g. i.v. bags).

The site may destroy and document destruction of unused study treatment, drug labels and packaging, as appropriate in compliance with site processes, monitoring processes, and per local regulation/guidelines. Otherwise, the Investigator will return all unused study treatment, packaging, drug labels, and a copy of the completed drug accountability log to the Novartis monitor or to the Novartis address provided in the Investigator folder at each site.

6.2.2 Handling of other treatment

The Investigator should instruct the participant/parent/guardian to notify the study site about any new medications he/she/their child takes after the participant was enrolled into the study. All medications, procedures and significant non-drug therapies (including physical therapy and blood transfusions) administered after the participant was enrolled into the study must be recorded.

The participant should be receiving optimal standard of medical care or surgical treatment for their HF and comorbidities.

6.2.3 Instruction for prescribing and taking study treatment

Novartis will supply the Investigators with all study medications required for the course of the study. Participants will be provided with bottles containing study drug corresponding to their assigned dose level, sufficient to last until the next scheduled visit (Table 1-2). Study drug will be supplied to participants as:

Sacubitril/valsartan tablets: 50 mg, 100 mg or 200 mg

Sacubitril/valsartan granules: 12.5 mg or 31.25 mg (3.125 mg/granule, either 4 or 10 granules packaged in capsule) supplied in a bottle

Sacubitril/valsartan liquid formulation (compounded by site / pharmacy) (refer to Pharmacy Manual)

Details regarding preparation of liquid formulation for sacubitril/valsartan are provided in the Pharmacy Manual.

Participants will be instructed to take their morning study drug doses between 6:00 and 09:00 (6-9 AM) and their evening study drug dose between 18:00 and 21:00 (6-9 PM). The study drugs (tablets) should be taken with a glass of water with or without food. For granules and liquid administration, see Pharmacy Manual.

All dosages prescribed and dispensed to the participant and all dose changes during the study must be recorded on the Dosage Administration Record (DAR) eCRF.

See Section 6.3 for Study treatment compliance.

6.3 Study treatment compliance

The Investigator must promote compliance by instructing the participant/parent/guardian to take/administer the study treatment exactly as prescribed and by stating that compliance is

necessary for the participant's safety and the validity of the study. The participant/parent/guardian must also be instructed to contact the Investigator if he/she is unable for any reason to take the study treatment as prescribed.

6.3.1 Recommended treatment of adverse events

Recommendations for handling Renal events, hypotension and hyperkalemia are described in Appendix 6, Appendix 8, and Appendix 9, respectively.

Medication used to treat adverse events (AEs) must be recorded on the appropriate eCRF.

6.4 Dose modification

6.4.1 Dose modifications

The maximum tolerated or target dose (dose level 4) will be maintained for the duration of the study. Both scheduled and unscheduled visits can be utilized for up-titration and/or down-titration throughout the study based on Investigator judgment.

For participants who are unable to tolerate the study drug, dose level adjustments and temporary interruptions of less than 3 months of study treatment are permitted. The following guidelines should be followed:

- The Investigator should adjust/interrupt/discontinue doses of concomitant medications if it is believed that they are the most likely cause of an adverse event.
- If adjustment/elimination of concomitant medications is not possible or does not alleviate the adverse event of concern, the Investigator may down-titrate to the next lower study drug dose level (Table 4-1) to temporary or permanent discontinuation of study drug.
- The participant may reinitiate the higher dose when the Investigator feels it is appropriate to do so per the directions provided below in this section.
- If the study drug is permanently discontinued, the participant should be discontinued from the study (Visit EOS).

Participants may be seen at any time for unscheduled visits during the study for re-evaluation of safety criteria parameters. Study drug dose level adjustments should mainly be based on overall safety and tolerability with focus on a) hyperkalemia, b) symptomatic hypotension and c) renal dysfunction. Laboratory assessments of serum sodium, potassium, creatinine, and eGFR (calculated based on the modified Schwartz formula (Schwartz, Work 2009) will be utilized. Refer to Appendix 6, Appendix 8, and Appendix 9 for treatment guidelines for renal dysfunction, management of hypotension and hyperkalemia, respectively.

Adjustment of study-drug dose level

During the study, down titration of the study drug at any time is allowed based on the safety and tolerability criteria defined in Table 6-2 and per the Investigator's clinical judgement.

The Investigator may down-titrate the study drug to the next lower dose level or may down-titrate 2 or 3 dose levels (e.g. from dose level 4 to dose level 1), based on their clinical judgement. If the tolerability issues are not alleviated despite down titration by multiple dose levels, the Investigator may temporarily discontinue study drug. Once the participant's condition is stable,

Clinical Trial Protocol (Version No. v00)

the participant can be up-titrated to the next higher dose level using unscheduled visits in an attempt to bring back the participant gradually to the target study drug dose level. The Investigator may select the next dose level for down- or up-titration according to his or her judgment (Table 4-1). For up-titration of the study drug, participants have to meet all criteria in Table 6-2 before administering the higher dose level.

Table 6-2 Safety monitoring criteria for adjustment of study-drug dose level

Parameter	Description
Potassium level	Serum K ≤ 5.4 mmol/L (mEq/L) or plasma K ≤ 5.0 mmol/L (mEq/L)
Kidney function	eGFR (calculated using the modified Schwartz formula) ≥ 30% mean GFR for age (Appendix 5, Table 10-4)
Kidney function	eGFR reduction < 35% compared to Visit Day1.
Blood pressure	Systolic blood pressure (SBP) > than the calculated 5 th percentile SBP for age as described in Appendix 7
AEs or conditions	No conditions that preclude continuation according to Investigator's judgment, including hypotension.

All changes should be recorded on the DAR eCRF.

Study drug restart after temporary treatment interruption

Participants who have temporarily discontinued study drug should be restarted as soon as possible as deemed appropriate by the Investigator. The Investigator should restart the participant on the study drug at the most appropriate dose level (Table 4-1) as per the Investigator's clinical judgment. If the participant does not tolerate the newly restarted studydrug dose level, they may be down-titrated again (if appropriate) or the study medication may be temporarily discontinued again.

Participants restarted on the study drug will retain their original study identification numbers.

Investigators may discontinue a participant's study drug due to serious or intolerable AEs suspected to be causally related to study drug. If study drug is discontinued for any reason, this must be recorded on the DAR eCRFs. In addition, participants who permanently discontinued study drug should be scheduled for the discontinuation study Visit EOS. Note that after a consecutive 3-month interruption of study treatment, participant should be discontinued from the study and should be seen at the site for Visit EOS).

If during study treatment interruption a participant requires treatment with an ACEI a \geq 36 hours washout should be observed before the ACEI is initiated. The ACEI must be discontinued ≥36 hours prior to restarting study drug. Participants who have temporarily discontinued study drug and are presently taking an ARB or a renin inhibitor must discontinue their current ARB or renin inhibitor on the day study drug is restarted.

If the participant becomes pregnant during the course of the study, the participant has to discontinue study drug immediately and should be seen at the site for Visit EOS and evaluated for transition to alternative treatment per the Investigator's clinical judgement.

Refer to (Section 8.4.5) for further details on pregnancies and reporting guidelines.

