10.3 Appendix 3: Clinical laboratory tests

10.3.1 Clinically notable laboratory values and vital signs

Table 10-1 Clinically notable laboratory values

Parameter	Conventional	SI Alert	SI
	Units	Value	Units
Hematology			
Red Blood Cell Count	x10E6/uL	>50% increase and > Upper limit of normal (ULN);	x10E12/L
		>30% decrease and < Lower limit of normal (LLN).	
Hemoglobin	g/dL	>50% increase and >ULN;	g/L
		(>30% decrease and <lln) <70.<="" any="" or="" td="" value="">	</lln)>	
Hematocrit	%	>50% increase and >ULN;	L/L
		>30% decrease and <lln.< td="">	</lln.<>	
White Blood Cell	x10E3/uL	>50% increase and >ULN;	x10E9/L
Count		>50% decrease and <lln.< td="">	</lln.<>	
Platelet Count	x10E3/uL	>75% increase and >ULN;	x10E9/L
		>50% decrease and <lln.< td="">	</lln.<>	
Chemistry			
BUN	mg/dL	>50% increase and >ULN	mmol/L
Creatinine	mg/dL	>50% increase and >ULN	umol/L
Albumin	g/dL	<20	g/L
Glucose	mg/dL	>50% increase and >ULN;	mmol/L
	· ·	(>50% decrease and <lln) <3.3.<="" any="" or="" td="" value="">	</lln)>	
Total Bilirubin	mg/dL	>100% increase and >ULN	umol/L
AST (SGOT)	U/L	>150% increase and >ULN	U/L
ALT (SGPT)	U/L	>150% increase and >ULN	U/L
Sodium	mEq/L	(>5% increase and >ULN) or any value >150;	mmol/L
		(>5% decrease and <lln) <125<="" any="" or="" td="" value="">	</lln)>	
Potassium	mEq/L	(>20% increase and >ULN) or any value >6;	mmol/L
	7	(>20% decrease and <lln) <3.<="" any="" or="" td="" value="">	</lln)>	
Chloride	mEq/L	>10% increase and >ULN;	mmol/L
	,	>10% decrease and <lln< td="">	</lln<>	
Calcium	mg/dL	>10% increase and >ULN;	mmol/L
	J	>10% decrease and <lln.< td="">	</lln.<>	
Uric Acid	mg/dL	>50% increase and >ULN	mmol/L

Increase and decrease are defined as compared to the baseline value of PANORAMA-HF OLE study (i.e. Visit 500).

Table 10-2 Criteria for clinically notable vital signs

Age	HR [min ⁻¹]	SBP [mmHg]	DBP [mmHg]	RR [min ⁻¹]
1-3 years	<60, >120	<76, >115	<45, >75	<14, >35
3-6 years	<55, >120	<82, >120	<50, >80	<12, >30

Novartis Confidential Page 54 of 66 Clinical Trial Protocol (Version No. v00) Protocol No. CLCZ696B2319E2

Age	HR [min ⁻¹]	SBP [mmHg]	DBP [mmHg]	RR [min ⁻¹]
6-12 years	<50, >105	<90, >130	<50, >80	<10, >27
>12 years	<45, >95	<90, >145	<55, >90	<8, >23

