10.5 Appendix 5: Renal safety monitoring

10.5.1 Specific Renal Alert Criteria and Actions and Event Follow-up

Table 10-3 Specific renal alert criteria and actions

Renal Event	Actions
eGFR decrease 25 – 49%	Consider causes and possible interventions
	 Repeat laboratory values within 48 hrs of receipt of abnormal test results. Assess patient for signs and symptoms of illness, acute kidney injury (AKI), etc.
eGFR decrease ≥ 50% *	Consider causes and possible interventions
OR if <18 years old, eGFR <	Repeat assessment within 24-48h if possible
35 mL/min/1.73 m ²	 Repeat laboratory values within 48 hrs of receipt of abnormal test results. Assess patient for signs and symptoms of illness, AKI, etc.
	 Consider drug interruption or discontinuation unless other causes are diagnosed and corrected
	Consider referral to nephrologist for diagnosis and management
	Consider patient hospitalization and specialized treatment
New onset dipstick proteinuria ≥ 3+	 Confirm presence of true proteinuria by quantification: protein:creatinine on first morning void
OR	Consider causes and possible interventions
Protein-creatinine ratio (PCR)	Assess serum albumin & serum total protein
≥ 1g/g creatinine (Cr)	Repeat assessment to confirm
	 Consider drug interruption or discontinuation unless other causes are diagnosed and corrected
	Consider referral to a nephrologist
New onset hematuria ≥ 3+ on urine dipstick	 Obtain urine microscopy to distinguish hemoglobinuria or myoglobinuria from hematuria
	Assess serum Cr
	 Exclude infection, trauma, calculi, bleeding from the distal urinary tract/bladder, menstruation
	Consider bleeding disorder

^{*} Corresponds to KDIGO criteria for Acute Kidney Injury

eGFR is calculated using a modified Schwartz formula for participants <18 years:

eGFR (ml/min/1.73m²) = 0.413 x height (cm) / serum creatinine (mg/dl). The most recently available height should be used for calculation.

eGFR decrease are defined as compared to the baseline value of PANORAMA-HF OLE study (i.e. Visit 500).

Urine samples for testing for renal monitoring, and particularly those for the PCR ratio determination, must be collected at the first morning void.

Table 10-4 GFR by age for up-titration

age (mL/min/1.73m ²)**	age (mL/min/1.73m ²)
≥ 31	< 31
≥ 38	< 38
≥ 30	< 30
2	≥ 31 ≥ 38

^{*} Age rounded to nearest whole number ** up-titration criteria

Source: (Peters, Gordon 1999)

10.6 **Appendix 6: Guidelines for the management of renal dysfunction**

General principles:

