Glomerular filtration rate in HF patients depends on intrinsic renal function and on a balance between afferent and efferent glomerular arterial tonicity. This tonicity is partly regulated by a stimulation of angiotensin II and could be affected by either study medication. Moreover, renal dysfunction may develop or may deteriorate in some patients after study drug administration. These recommendations have been developed to guide the investigators in managing patients with renal dysfunction after enrollment and the first dose of sacubitril/valsartan.

Two types of response to serum creatinine increase are described:

Surveillance situation

If, at any time after enrollment and the first open-label dose of sacubitril/valsartan, eGFR%* decreases by $\geq 50\%$ from baseline in PANORAMA-HF OLE study (i.e. Visit 500), the investigator will check for potentially reversible causes of renal dysfunction such as:

- non-steroidal anti-inflammatory drug intake, antibiotics, or other treatments known to cause creatininemia
- volume decrease, including that resulting from excessive dosing of diuretics
- urinary infection
- urinary tract obstruction
- study medication

Action situation

If a patient eGFR* decreases by ≥ 50% from baseline of PANORAMA-HF OLE study (i.e. Visit 500) (or if serum creatinine concentration rises above 3 mg/dL (265 µmol/L), the investigator will check for potentially reversible causes of renal dysfunction (see above). If the investigator judges that study medication has to be stopped, he/she will have to contact the Novartis medical monitor or his/her designee. Thereafter, serum creatinine assessments will have to be repeated at least each week until levels return to acceptable values. If study medication was stopped, every effort will be done to restart it again, according to clinical conditions.

*eGFR is calculated using a modified Schwartz formula for participants <18 years.

For participants ≥18 years, an adult formula for eGFR will be utilized (Reference: Novartis Nephrology Guidance document)

10.7 Appendix 7: American heart association (AHA) pediatric advanced life support (PALS) guidelines

Table 10-5 5th percentile systolic blood pressure (SBP) table

Age	SBP percentile	SBP (mmHg)
1 month to < 1 year	5 th	70
1 year	5 th	72
2 years	5 th	74
3 years	5 th	76
4 years	5 th	78
5 years	5 th	80
6 years	5 th	82
7 years	5 th	84
8 years	5 th	86
9 years	5 th	88
10 years	5 th	90
11 years	5 th	90
12 years	5 th	90
13 years	5 th	90
14 years	5 th	90

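### The up-titration checklist counts eGFR loss from Visit Day1 and the renal alerts count it from Visit 500, with no linking rule, so a numeric stop or a 48-hour repeat test can be missed

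*Protocol*

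**What the plan says.** Protocol Section 6.4.1 makes Table 6-2 a checklist: "For up-titration of the study drug, participants have to meet all criteria in Table 6-2 before administering the higher dose level". Two of its rows are numeric and renal. One is absolute: eGFR must reach 30% of the mean GFR for age, and the Table 10-4 floors are 30, 31 and 38 mL/min/1.73 m². The other is relative: "eGFR reduction < 35% compared to Visit Day1". No local sample is taken at Visit Day1, so the Day1 value is the central Visit 599 result (Table 1-2 footnote 6; Section 8.4.4).

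The same table supports dose reduction: "down titration of the study drug at any time is allowed based on the safety and tolerability criteria defined in Table 6-2". The return towards target dose is conditional: "Once the participant's condition is stable". A last row leaves room for investigator judgement.

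The renal alert rules use an earlier reference:

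- Table 10-3 (Appendix 5): "eGFR decrease are defined as compared to the baseline value of PANORAMA-HF OLE study (i.e. Visit 500".
- Appendix 6, action situation: eGFR "decreases by ≥ 50% from baseline of PANORAMA-HF OLE study (i.e. Visit 500".
- Table 10-1, which includes creatinine: "Increase and decrease are defined as compared to the baseline value of PANORAMA-HF OLE study (i.e. Visit 500".

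Table 10-3 has a row for a 25–49% decrease. A second row covers a decrease of 50% or more, or eGFR below 35 in a participant under 18. Both carry the instruction "Repeat laboratory values within 48 hrs of receipt of abnormal test results". The second also asks the investigator to consider interrupting or stopping the drug.

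Sections 6.4.1 and 6.4.2 point to these appendices. Neither says how the two references relate, or whether an alert bars an increase.

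**The concern.** Each rule is clear alone, but eGFR can move between Visit 500 and Visit Day1, and the two percentages then describe different falls.

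- **Day1 well below Visit 500.** The Day1 comparison looks mild while the cumulative loss is large. The mandatory checklist then has no numeric renal stop for a child who meets the protocol's own 50% trigger.
- **Day1 well above Visit 500.** A large fall during this study looks small against Visit 500, and the timed repeat test is not prompted.

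Renal dysfunction is one of three named drivers of dose adjustment in Section 6.4.1, and renal impairment is an event of special interest in SAP Section 2.7.1.1. Scheduled on-treatment laboratory tests are six months apart (M6, M12), because M3 and M9 are telephone visits. Without an unscheduled test or an earlier end-of-study visit, the next value may be six months away.

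The potassium row shows that the checklist and the appendices can be aligned. Table 6-2 allows up-titration up to a serum value of 5.4 mmol/L, and the Appendix 9 tier that raises temporary discontinuation starts just above 5.4.

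**Working it through.** The plan states no figure to reproduce, so the check is threshold algebra.

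**Inputs.** The 35% limit and the absolute floors come from Tables 6-2 and 10-4. The 25%, 50% and 35 mL/min/1.73 m² limits come from Table 10-3. Let *r* = Day1 eGFR / Visit 500 eGFR and *x* = current eGFR / Visit 500 eGFR. All eGFR values and ratios below are assumptions for illustration.

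**(a) Numeric renal rows pass at a fall of at least 50% from Visit 500**

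- The relative row passes if *x* > 0.65*r*. The upper alert tier is met if *x* ≤ 0.50.
- Both hold only if 0.65*r* < 0.50, so *r* < 0.50/0.65 = 0.769.
- The absolute floor must also be met. At a fall of exactly 50%, Visit 500 eGFR must be at least 30/0.50 = 60 for the lowest floor and 38/0.50 = 76 for the highest.
- Example: Visit 500 = 100, Day1 = 70, now 48. From Day1: 1 − 48/70 = 31.4%, which passes. From Visit 500: 1 − 48/100 = 52%, which meets the upper tier. The value 48 clears all three floors.

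| *r* | Overlap, current eGFR as % of Visit 500 | Width (points) |
|---|---|---|
| 0.75 | 48.75–50 | 1.25 |
| 0.70 | 45.5–50 | 4.5 |
| 0.60 | 39–50 | 11 |

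**(b) In-study fall beyond 35% with no percentage alert**

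- The relative row fails if *x* ≤ 0.65*r*. No percentage alert fires if *x* > 0.75.
- Both hold only if 0.65*r* > 0.75, so *r* > 0.75/0.65 = 1.154.
- Example: Visit 500 = 80, Day1 = 110, now 70. From Day1: 1 − 70/110 = 36.4%. From Visit 500: 1 − 70/80 = 12.5%. The value 70 is also above the absolute limit of 35, so no eGFR row of Table 10-3 fires.
- Creatinine at unchanged height is 80/70 = 1.14 times Visit 500, so the Table 10-1 flag (an increase above 50%, and above normal) is silent. Because eGFR is proportional to height/creatinine, height would have to exceed 1.5 × 70/80 = 1.31 times its Visit 500 value before creatinine passed +50%.

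| *r* | Gap, current eGFR as % of Visit 500 | Width (points) |
|---|---|---|
| 1.20 | 75–78 | 3 |
| 1.375 | 75–89.4 | 14.4 |
| 1.50 | 75–97.5 | 22.5 |

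**Common reference (*r* = 1).** Gap (a) would need *x* > 0.65 and *x* ≤ 0.50. Gap (b) would need *x* ≤ 0.65 and *x* > 0.75. Neither is possible, so both gaps come from the two references and not from the cut-offs. This treats the Table 10-3 tiers as contiguous. Read literally, a 49.5% fall meets neither percentage row under any reference, which is a separate and minor matter.

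**The case against.** The strongest reply is that nothing conflicts. Table 6-2 sets necessary conditions: passing it permits an increase and never requires one. Table 10-3 and Appendix 6 run alongside as alert and work-up rules, and all can be obeyed together. An in-study reference for titration plus an earlier one for cumulative decline is a coherent choice, although the protocol does not give that reason.

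Much of this stands. In (a) the work-up for a 50% fall still fires. At *r* ≤ 0.75 the Visit 599 result itself already lies at least 25% below Visit 500, so the child is usually known to be at risk. The judgement row, the stability condition and the Section 7.1 stopping provisions can all prevent the increase. In (b) up-titration is blocked and down-titration allowed. Section 8.4.4 makes the investigator review every result, and Section 8.6.1 asks for attention to marked change since baseline or the last visit. Part of the apparent fall may be loss of an earlier rise, or a central-to-local assay difference.

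None of these safeguards supplies the missing item: a numeric renal stop in (a), or a timed repeat in (b).

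Three stronger readings are tempting but unsupported:

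- **The rules contradict each other.** They do not, as explained above.
- **A halving of eGFR in this study would go unnoticed.** With *x* = 0.5*r*, the fall from Visit 500 is 1 − 0.5*r*. It stays below 25% only if *r* > 1.5. At *r* = 1.2 it is 40% and meets the lower alert row.
- **An alert at a 25% to under 35% fall, while up-titration stays open, is an error.** That is how the tiers are built and would occur with a single reference.

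**Conclusion.** The point holds as a gap in the safety rules. Two references with no linking rule leave one numeric stop missing when Day1 is below 76.9% of Visit 500, and one timed repeat test missing when Day1 is above 115.4% of it. The affected bands are narrow near those limits and widen as the ratio moves away from them.

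The algebra is certain, but the practical weight is not. The documents give no Visit 500 or Day1 eGFR values, at most 8 children enrol, and each must be judged safe to enrol. Gap (b) is shown only for the Table 10-3 prompt, so it gives no ground for rewriting the Appendix 6 triggers. A reader might infer that the trial's results are at risk. They are not: the SAP summarises adverse events and only lists laboratory values, so no planned analysis uses these thresholds. Nor do the documents show that any child has been or would be harmed. This is a cheap improvement of low priority.

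**What to change.** 1. **Table 10-3.** Define the percentage eGFR decrease as the larger of the decrease from Visit 500 and the decrease from Visit Day1 (the Visit 599 central result). In example (b) the governing figure becomes 36.4%, and the 48-hour repeat is prompted.
2. **Table 6-2.** Add a row: no up-titration while eGFR is at least 50% below Visit 500, unless a different cause has been found and corrected and the medical monitor has been consulted. The exception keeps the row in line with Table 10-3. An unconditional bar would be stricter than the protocol's own tier and could hold a stable child below target dose.

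The sponsor's clinical team should confirm the wording.

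**Cost.** Two tables change. No new baseline data are needed, because current rules already require both values. A few extra repeat tests will follow, some caused by central-to-local assay differences, and there is slightly less freedom to up-titrate. In example (b) the alert would start at 0.75 × 110 = 82.5 instead of 0.75 × 80 = 60. When *r* exceeds 1/0.75 = 1.33, it can therefore fire in a child still at or above the Visit 500 value. That is acceptable for a prompt to retest, but sites should be told to expect it.
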